5.2 EXCLUSION CRITERIA

An individual who meets any of the following criteria will be excluded from participation in this study:

- 1) Any prior use of the study test article.
- 2) Any clinically significant weight loss any time in prior 4 weeks at discretion of Investigator based on medical history interview.
- 3) Subjects with any of the following are not eligible:
 - a. Previous history of QTc prolongation resulting from “known-risk” medications (www.Crediblemeds.org) that required discontinuation of that medication;

- b. Congenital long QT syndrome, or 1st degree relative with unexplained sudden death under 40 years of age;
- c. Presence of left bundle branch block (LBBB);
- d. QTc with Fridericia's correction (QTcF) that is unmeasurable, or ≥ 480 msec on screening ECG. The average QTcF from the screening ECG (completed in triplicate) must be < 480 msec in order for the subject to be eligible for the study.

4) Subjects must not have had a clinically significant cardiac event such as myocardial infarction (within 6 months prior to the first dose of the study treatment); uncontrolled/symptomatic congestive heart failure (New York Heart Association (NYHA) classification of heart disease, Class III or IV, see Appendix 3) within 6 months before entry; or the presence of any other uncontrolled cardiovascular conditions [unstable hypertension at discretion of Investigator or arrhythmia, unstable angina pectoris, or severe valvular heart disease, etc.] that, in the opinion of the Investigator, increases the risk of ventricular arrhythmia.

5) Subjects with a history of arrhythmia (multifocal premature ventricular contractions (PVCs), bigeminy, trigeminy, ventricular tachycardia, or uncontrolled atrial fibrillation) which is symptomatic or requires treatment (CTCAE Grade 3) or asymptomatic sustained ventricular tachycardia are not eligible. Subjects with atrial fibrillation with well-controlled ventricular rate are eligible at the discretion of the Investigator.

6) Psychiatric conditions, social situations or substance abuse that precludes the ability of the subject to cooperate with the requirements of the trial and protocol therapy at Investigator discretion.

7) Inability to refrain from alcohol consumption for 48 hours prior to day 1 and for the duration of the study. Illicit drugs, including THC, must be avoided from screen through the duration of the study.

8) Grade 2 or higher peripheral neuropathy.

9) Positive results for Hep B surface antigen, Hep C antibody, or HIV 1/2 antibody at screening visit.

10) Clinically significant immunodeficiency disorder in the opinion of the Investigator.

11) Pregnancy or women of childbearing potential and men who are sexually active and not willing/able to use medically acceptable forms of contraception.

12) Women who are breastfeeding are not eligible for this study.

13) Subjects that are vegan, vegetarian or consume a soy-rich diet.

14) Any history of systemic infection requiring hospitalization, systemic antibiotics, or as judged clinically significant by the investigator in the 3 months prior to day 1.

15) Any condition possibly affecting drug absorption (e.g., prior bariatric surgery, gastrectomy, intestinal resection). Participants who have undergone appendectomy or cholecystectomy are allowed so long as the surgery occurred more than 6 months prior to day 1.

16) Treatment with another investigational drug within 30 days or 5 half-lives (whichever is longer) proceeding Day 1.

17) Positive drug screen or alcohol test at screen and day 1 predose.

18) Blood donation of approximately 1 pint (500 ml) or more within 60 days of day 1; plasma donations within 14 days of day 1. Subjects must agree not to donate blood or plasma for the duration of the study and for 30 days following end of study procedures.

19) Inability to swallow powdered medication followed with water.

20) History of sensitivity to heparin or heparin-induced thrombocytopenia.

21) Considered by the Investigator to be unsuitable to participate in the study for any other reason.

5.3 LIFESTYLE CONSIDERATIONS

Participants will be counseled to adhere to a low isoflavone diet, such as those listed in **Appendix 1**, during the dosing and PK/PD assessment period. It is important for study participants to maintain a low isoflavone diet (e.g., low soy-diet) in order to accurately quantify study drug pharmacokinetics and drug exposure.

Contraception:

- 1) Women who are not able to get pregnant are not required to use birth control. To be considered not able to get pregnant, you must be
 - a) postmenopausal for at least 12 months confirmed by hormone testing; **or**
 - b) surgically sterile
 - hysterectomy (surgical removal of uterus)
 - bilateral tubal ligation (tubes "tied")
 - removal of both ovaries and/or fallopian tubes
- 2) Women who are able to get pregnant must
 - a) have a negative urine pregnancy test at screening and on admission to CRU; **and**
 - b) must be using, and agree to continue using, an effective method of contraception for at least 4 weeks prior to first study drug administration until 7 days after the last dose of study drug.

Effective methods of contraception include the following:

- 1) Total abstinence from sexual intercourse with a partner that may result in pregnancy
- 2) Sexual intercourse with a partner who has had a vasectomy
- 3) Non-Hormonal Intrauterine device
- 4) Double barrier contraception, i.e., condom and diaphragm, or condom or diaphragm with spermicidal gel or foam.
- 5) Women using hormonal contraception below must agree to use a barrier or other effective method of contraception during the study
 - a) Combined (estrogen and progestogen containing) hormonal contraception
 - oral
 - intravaginal
 - transdermal
 - b) Progestogen-only hormonal contraception
 - oral
 - injectable
 - implantable

Women must not donate ova (eggs) during the study and for at least 30 days after the last dose of study drug.

Male subjects who have not had a vasectomy and/or subjects who have had a vasectomy but have not had 2 post-surgery negative tests for sperm whose partners are not on a highly effective method of contraception (hormonal contraception is sufficient for female partners) must agree to use an acceptable method of contraception from time of first dose of study drug until 30 days after the last dose of the study drug, and must not donate sperm during the study and for at least 30 days after the last dose of study drug.

5.4 SCREEN FAILURES

Screen failures are defined as participants who consent to participate in the clinical trial but are not subsequently entered in the study due to their inability to meet inclusion or exclusion criteria or their decision to not consent to enrollment. A minimal set of screen failure information is required to ensure transparent reporting of screen failure participants, to meet the Consolidated Standards of Reporting Trials (CONSORT) publishing requirements and to respond to queries from regulatory authorities. Minimal information includes demography, screen failure details, eligibility criteria, and any serious adverse event (SAE).

5.5 STRATEGIES FOR RECRUITMENT AND RETENTION

Recruitment of subjects will be performed by the clinical site who maintains a robust database of healthy volunteers. The site will outreach to potential participants to encourage screening.

For optimal recruitment and retention, subject contact and convenience will be prioritized. Examples include providing effective subject information on the study, providing face-to-face meetings for discussing the study and questions, and ensuring the study design places no significant burden to being involved in the research study.

Subjects will be in contact with the study through clinical visits. Subject outreach will occur to encourage continued compliance and participation in clinic visits during the repeat dose study period.

6 STUDY INTERVENTION

The study intervention being investigated under this protocol is BIO 300 Oral Powder, an amorphous solid dispersion of synthetic genistein.

6.1 STUDY INTERVENTION(S) ADMINISTRATION

6.1.1 STUDY INTERVENTION DESCRIPTION

BIO 300 Oral Powder will be provided by Humanetics Corporation, Minneapolis, Minnesota. BIO 300 Oral Powder is an amorphous solid dispersion of genistein. It is packaged in single use foil sachets containing 500 mg genistein. It is a free-flowing pale orange to slightly tan powder.

6.1.2 DOSING AND ADMINISTRATION

Single Ascending Dose Cohorts:

Cohort 1 dose: one BIO 300 Oral Powder sachet, 500 mg genistein

Cohort 2 dose: two BIO 300 Oral Powder sachets, 1000 mg genistein (2X the dose of Cohort 1 in the absence of dose-limiting toxicity [DLT])

Cohort 3 dose: four BIO 300 Oral Powder sachets, 2000 mg genistein (2X the dose of Cohort 2 in the absence of DLT)

Cohort 4 dose: TBD based on the observed PK and AE profiles in the first 3 dose cohorts

All single dose cohorts will be administered the drug at the clinic under the supervision of the study personnel. Subjects will follow a diet low in soy isoflavones for 7 days before and 7 days after treatment and will fast at least 8 h before dosing. Subjects will remain fasted for 4 hours after the test article

administration. Subjects will remain in the clinic 12 hours after dosing. Subjects will be provided a standardized low soy meal after the 4-hour blood draw and after the 8-hour blood draw. The purpose of fasting is to standardize the effect of food on PK and PD markers.

Multiple Single Dose Cohort:

The cohort 5 dose will be dosed daily for 6 consecutive days at the highest dose or the maximum tolerated dose from the Single Ascending Dose cohorts. Subjects will consume the test article each day within +/- 2 hours of time when the first dose was administered and not within 1 hour before or after eating. The Day 6 dose will be administered during clinic visit 7 so that PK and PD blood draws can be timed after the dose.

Drinking of room temperature water only, (up to 240 mL) will be encouraged following administration of each BIO 300 Oral Powder sachet.

Subjects will follow a diet low in soy isoflavones for 7 days before treatment, during the 6 days of treatment and 7 days after treatment. Subjects will fast at least 8 h before the first dose, 3rd dose and the 6th dose. Subjects will remain in the clinic 4 h after the first dose and 12 hours after the 6th dose. Subjects will remain fasted for 4 hours after the test article administration on days 1 and 6. On the 6th day, subjects will be provided a standardized low soy meal after the 4-hour blood draw and after the 8-hour blood draw. The purpose of fasting is to standardize the effect of food on PK and PD markers.

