Open-label, single dose given daily for 6 days in healthy volunteers. A single cohort will enroll 14 subjects (7M/7F) of which 4 will be backups (2M/2F), so that at least 8 subjects (4M/4F) complete the protocol procedures. Subjects will follow a diet low in soy isoflavones for 7 days before treatment, during the 6 days of treatment and 7 days after treatment. Subjects will fast at least 8 h before the first dose, 3rd dose and the 6th dose. The test article will be administered starting on day 1 and the dose used in this study will be determined based on safety and PK analysis from the single ascending dose study. Subjects will be administered test article daily during their schedule clinic visits. Subjects will remain in the clinic 4 hours after the first dose and 12 hours after the 6th dose for observations and blood sample collection for clinical lab assessment, PK and PD. Subjects will remain fasted for 4 hours after the test article administration on days 1 and 6. On the 6th day, subjects will be provided a standardized low soy meal after the 4-hour blood draw and after the 8-hour blood draw. Blood sampling and/or observations will be performed on dosing days 1-6 as described in the schedule of events. Subjects will return to the clinic on days 7, 8 and 13 after initial dosing for blood sampling and/or observations as detailed in the schedule of events. Subjects may not miss any clinic visits. At the conclusion of the study, data will be analyzed to determine safety and PK, and data will be analyzed from all cohorts to determine PD.

Objectives:

Primary Objectives:

- Determine the overall adverse event and PK profiles of single ascending doses of BIO 300 Oral Powder in healthy volunteers
- Determine the overall adverse event and PK profile of multiple doses of BIO 300 Oral Powder in healthy volunteers

Secondary Objectives:

- Determine the effects of single and multiple doses of BIO 300 Oral Powder on blood-based biomarkers
- Use a combination of the PK and PD profiles from the single and multiple doses of BIO 300 Oral powder to identify the putative BIO 300 Oral Powder human efficacious dose

Endpoints:

Primary

Evaluate the safety and pharmacokinetics of BIO 300 Oral Powder in Healthy Volunteers

Secondary

Characterize the expression of blood-based biomarkers

Study Population:

[figure not shown]

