4 STUDY DESIGN

4.1 OVERALL DESIGN

[figure not shown]
- Open label, single site phase 1 study in healthy volunteers who are equally distributed by sex.
- The study will include a single ascending dose (SAD) study in four cohorts and will be followed by a six-day multiple single dose study at either the highest dose or the maximum tolerated dose.
- There are no planned stratifications or sub-studies.

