7.5 DOSE ESCALATION CRITERIA

A Safety Monitoring Committee (SMC) consisting of a Humanetics representative, the Medical Monitor and Principal Investigator, or their recognized delegates will review all available data. The determination for escalation to the next Cohort will require, at a minimum, a review of all safety data of 6 subjects in the previous SAD Cohort through at least Day 3. Decisions to proceed with dose escalations, adding additional subjects to the current Cohort, and possible dose adjustments will be made following this review with the Medical Monitor and Principal Investigator agreeing with the decision. Whether additional information such as PK or PD data may be needed before a decision to escalate can also be determined by the SMC. The primary responsibility of the SMC is to regularly monitor the overall safety of patients enrolled in the study, while protecting the scientific integrity of the study data. Dose escalation criteria will be the following:

- Dose escalation may occur if no more than 2 subjects in a 6-subject cohort experiences a dose-limiting toxicity (DLT, as defined below).
- If 3 DLTs occur (3/6 subjects), an additional 2 subjects will be treated with the same dose.
- If no additional DLTs occur (3/8 subjects), dose escalation may proceed.
- The study sponsor will temporarily cease enrollment for evaluation if in any given cohort 4/8 subjects experience DLTs attributable to BIO 300 Oral Powder as the MTD (maximum tolerated dose) will have been exceeded and no further dose escalation will occur.

DLT is any grade 3 or grade 4 adverse event listed in the draft FDA document entitled "*Toxicity Grading Scale for Healthy Adult and Adolescent Volunteers Enrolled in Preventive Vaccine Clinical Trials*."

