Investigational Agent: BIO 300 Oral Powder

Phase of Development: Phase 1

Sponsor: Humanetics Corporation

Design: Open label, single site phase 1 study in healthy volunteers who are equally distributed by sex. The study will include a single ascending dose (SAD) study in four cohorts and will be followed by a six-day multiple single dose (MSD) study at either the highest dose or the maximum tolerated dose. There are no planned stratifications or sub-studies.

This Statistical Analysis Plan (SAP) details the planned methods for summarizing data collected in the clinical study conducted under Humanetics Corporation protocol CL0106-01. The current study protocol is identified as version 1.0 dated 16-Nov-2020.

Future protocol amendments (if any) will be reviewed to assess whether the changes necessitate modification of this SAP.

Since the study protocol is a companion document to this SAP, aspects in the protocol unrelated to statistical issues (e.g., patient eligibility criteria and detailed BIO 300 Oral Powder information) are not repeated here.

2. Study Objectives

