5.4. Pharmacodynamics (PD) Population

The PD Population will include all subjects who receive at least 1 dose of BIO 300 Oral Powder and have sufficient, valid serum samples to estimate key parameters for at least 1 of the days of sampling. PD summaries will be based on the PD population.

6. Safety Monitoring Committee

A Safety Monitoring Committee (SMC) will review safety and PK data (when available) during the conduct of the study. After each cohort in the SAD study, the SMC will make decisions on proceeding with dose escalation, adding additional subjects to the current cohort, and possible dose adjustments. The SMC may also recommend stopping the study, suspending enrollment or significant changes to the dosing regimen and/or enrollment if warranted by safety data. The SMC will immediately communicate this recommendation to Humanetics for review and determination of a final decision. SMC data reviews are

not considered interim analyses and do not necessitate adjusting of the alpha level for multiple statistical hypothesis tests.

7. Statistical Methods

Unless stated otherwise, the term “descriptive statistics” refers to the number of subjects (n), mean, median, standard deviation (STD), minimum (min), and maximum (max) and standard errors/confidence intervals for continuous response variables and distribution tables or histograms for discrete response variables. Min and max values will be rounded to the precision of the original value, means and medians will be rounded to 1 decimal place greater than the precision of the original value, and STDs will be rounded to 2 decimal places greater than the precision of the original value. Percentages will be rounded to the nearest whole number (zeros are not displayed) with values of “< 1%” and “> 99%” shown as necessary for values falling near the boundaries.

The computed change from baseline will be calculated for all measured variables and expressed as the mean change from baseline + STD of the change from baseline. Analysis of covariance will be used to compare dosage groups on “change from baseline” measures (with baseline measurement considered as an adjustment covariate).

Unless otherwise note, all data collected during the study will be included in data listings and will be sorted by study cohort, subject number and then by visit for each subject number.

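### A dose with DLTs in 3 of 8 volunteers after one dose is eligible for cohort 5's six daily doses, with no repeat-dose limit and no required cohort 4 PK

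*Combined protocol and SAP*

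**What the plan says.** Three places set the cohort 5 dose by the same rule. Protocol section 4.1 describes a "six-day multiple single dose study at either the highest dose or the maximum tolerated dose". Section 6.1.2 has the cohort "dosed daily for 6 consecutive days at the highest dose or the maximum tolerated dose from the Single Ascending Dose cohorts". The SAP's opening design statement likewise has the "study at either the highest dose or the maximum tolerated dose".

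The protocol synopsis (section 1.1) words it differently: "the dose used in this study will be determined based on safety and PK analysis from the single ascending dose study". It gives no criterion.

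The MTD has no definition of its own; its meaning comes from section 7.5. Up to 2 DLTs in 6 subjects allow escalation, and 3 in 6 bring in two more subjects at the same dose. Then: "If no additional DLTs occur (3/8 subjects), dose escalation may proceed". Enrolment pauses, and escalation ends, when "4/8 subjects experience DLTs attributable to BIO 300 Oral Powder as the MTD (maximum tolerated dose) will have been exceeded". A DLT in that section is a grade 3 or 4 event on the FDA vaccine-trial toxicity scale.

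On PK, section 7.5 says: "Whether additional information such as PK or PD data may be needed before a decision to escalate can also be determined by the SMC". SAP section 6 has the SMC "review safety and PK data (when available) during the conduct of the study" and make decisions after each SAD cohort, including possible dose adjustments. The one planned interim safety and PK analysis (protocol 9.4.6, SAP 7.4) uses cohorts 1 to 3 and sets the cohort 4 dose.

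**The concern.** The escalation bar was written to decide whether a new group may receive a higher single dose. Through the highest-dose-or-MTD rule it also becomes the only numeric limit on the dose that another group takes six times. Those subjects are healthy volunteers for whom the protocol proposes no benefit (section 2.2.2).

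Repeat dosing can raise exposure above the single-dose level, and section 8.1 lists a drug accumulation index among the PK parameters. PK at the candidate dose therefore bears directly on the choice. That dose may well be the cohort 4 dose, whose PK lies outside the one planned interim analysis. Within cohort 5, PK samples are taken to 4 hours on day 1 and then not until day 6, so exposure across doses 2 to 5 is not measured. The decision before the first dose is the best place to control it.

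**Working it through.** **Inputs from the documents.** Section 7.5: at most 2/6 DLTs clears; 3/6 adds two subjects; 3/8 clears; 4/8 exceeds the MTD. Sections 4.1, 6.1.2 and the SAP design statement: cohort 5 at the highest SAD dose or the MTD. The plan gives no operating characteristics for these counts and no target DLT rate. Its only nearby derived figure, at least 32 completers, reproduces: 4 × 6 + 8 = 32.

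**Step 1: is 3/8 eligible?** 3/8 = 37.5%, below the 4/8 = 50% at which the MTD is exceeded. There are two routes to cohort 5. Cohort 4 may finish at 3/8 and be the highest dose. Or an earlier cohort may finish at 3/8 and the next exceed the MTD, leaving the 3/8 dose as the MTD. No stricter limit for repeat dosing appears in either document.

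**Step 2: how much does the bar filter?** The true DLT rate p is assumed, because the documents give none.

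P(clear) = P(X ≤ 2; n = 6, p) + P(X = 3; n = 6, p) × (1 − p)²

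| Assumed p | By ≤ 2/6 | Only by 3/6 then 3/8 | Total |
|---|---|---|---|
| 0.20 | 0.9011 | 0.0524 | 0.9535 |
| 0.333 | 0.6804 | 0.0975 | 0.7779 |
| 0.375 | 0.5960 | 0.1006 | 0.6966 |
| 0.40 | 0.5443 | 0.0995 | 0.6439 |

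(Totals are sums of unrounded terms.) These are chances of clearing escalation on the counts alone, not chances that cohort 5 receives the dose.

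**Step 3: how precise is the observed result?** Exact 95% intervals: 3/8 gives 8.5% to 75.5%; 2/6 gives 4.3% to 77.7%.

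**Step 4: accumulation, illustrative.** For linear, single-exponential decline, six doses 24 h apart accumulate by (1 − k⁶)/(1 − k), with k = 2^(−24/t½). Half-lives are assumed:

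- 8 h: k = 0.125, ratio 1.14
- 12 h: k = 0.25, ratio 1.33
- 24 h: k = 0.5, ratio 1.97

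**Step 5: cost of barring the 3/8 route.** P(X ≥ 3; n = 6) is 0.0022 at p = 0.05 and 0.0159 at p = 0.10. This overstates the added cost, since section 7.5 already stops some of these doses. The part that would otherwise have cleared is 20p³(1 − p)⁵, which is 0.0019 and 0.0118.

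**The case against.** A reader might infer that no scheduled review includes cohort 4. The documents do not support that. SAP section 6 has the SMC decide after each SAD cohort, and cohort 4 is one. SAP 7.4 plans no further interim analyses, but it also says that SMC reviews are not interim analyses, so a review's absence from 7.4 shows nothing.

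A reader might also infer that a 3/8 dose must go forward. Section 7.5 only permits escalation, with the Medical Monitor and Principal Investigator agreeing. The SMC may adjust doses or recommend changes to the regimen, and individual stopping (7.1), withdrawal (7.3) and study suspension (10.1.2) all remain.

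The synopsis can fairly be read as already requiring SAD-wide safety and PK, and as compatible with 6.1.2: one names the target dose, the other the evidence. This largely stands, but the synopsis supplies neither a procedure nor a criterion.

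The strongest statistical objection is that barring 3/8 while keeping 2/6 draws a fine line. The 2/6 interval has the higher upper limit, and at assumed rates of 33% and 40% the tighter bar still clears 68% and 54% of doses. This stands: the bar is a modest guard. Nor do the documents support true rates of 20% to 40%; section 2.2.3 describes an exceptional safety record.

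The no-DLT wording in section 6.1.2 does not close the gap. It conditions only the doublings into cohorts 2 and 3.

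**Conclusion.** The concern holds in a limited form. On the written rules, a dose with DLTs in 3 of 8 volunteers after one administration is eligible for six daily doses. Beyond that, three things are missing: a requirement for cohort 4 PK before cohort 5, an SMC decision that names the cohort 5 dose, and a tolerability limit for repeat dosing. SMC discretion is real and is the main protection, but its PK input is optional in section 7.5 and depends on availability in SAP section 6.

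The eligibility finding rests on the text alone. The sizes are illustrative: 5 to 10 percentage points of clearance through the 3/8 route at assumed DLT rates of 20% to 40%, and 1.14- to 1.97-fold accumulation at assumed half-lives of 8 to 24 h. No DLT counts are reported, so whether a 3/8 result arose is unknown. The amendment history shows that Cmax from all four SAD cohorts was in hand by version 2.0. That makes a full PK review feasible; it does not show that the plan required one.

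**What to change.** 1. Align protocol sections 4.1 and 6.1.2 and the SAP design statement with the synopsis.
2. Add to protocol section 7.5 and SAP section 6 that, before the first cohort 5 dose, the SMC must select that dose from the safety and PK of all four SAD cohorts. It may go below the highest dose or the MTD on safety or predicted repeat-dose exposure. This is the main part of the change.
3. State that a dose cleared only through the 3/6-to-3/8 expansion is not eligible for repeat dosing.

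The cost is wording plus one defined SMC decision, with no new subjects or samples. Cohort 5 may start slightly later, while cohort 4 PK is completed, or may run at a lower dose. At a true DLT rate of 5% to 10%, the bar in item 3 would step a dose down in at most 0.2% to 1.6% of cases.
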